Posters displayed on admitting wards notify parents and patients that the centre is participating in a national service evaluation of children's bone and joint infections. Parents will have the opportunity to inform a member of their child's care team if they do not want their child's information entered into the database.

Sample size calculations

The study is funded to enable a maximum of 1,000 cases of OM or SA to be entered into the database. In order to get an accurate national evaluation, all participating centres will be asked to record cases for at least six months. It is estimated that at least 500 cases will be accrued by around 50 centres over a 6-12 month period. All eligible cases at participating centres will be recorded.

Data Collection

We will record demographic details and details of hospitalisation(s) including transfers between hospitals; type and site of disease; routine haematology, biochemistry and microbiology; radiological procedures; surgical procedures; length of IV therapy; antimicrobials used, route and duration; reason/criteria; used for oral switch (if any); and clinical outcomes at 3 months.

These data are to be collected from the patients' clinical notes. Training will be provided for teams at participating centres. The study will use a password protected web based data collection form that can be accessed at all participating hospitals.

Study Objectives

The study has three major objectives:

1. What are the clinical, biochemical and radiological criteria used by UK paediatricians / orthopaedic surgeons / radiologists to diagnose osteomyelitis?
2. What is the range of durations of intravenous and oral antibiotics used to treat osteomyelitis? What factors affect durations (e.g. surgery / blood tests / microbiology results).
3. What are the rates of treatment failures / complications for different:
 - (a) Antibiotic regimes used at participating centres?
 - (b) Surgery types used at participating centres?

and what actions were taken following a complication at participating centres?

These objectives are broken down into further sub-objectives:

- 1A:** Describe the study sample: demographics; past medical history; presenting limbs/joints affected; and diagnosis types aiming to identify factors predisposing children to bone and joint infections. Describe pre-presentation variables that affect drug choice, dosage and duration, in particular age, allergies and co-morbidities.

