- 1B:** Describe the clinical time-line for diagnosis: summarising the number of days from presentation when key clinical actions (1st imaging, surgery and initiation of IV antibiotics) occur.
- 1C:** Describe the surgical procedures carried out prior to diagnosis.
- 1D:** Summarise the types of microbiological tests carried out and the types of samples taken. Specifically, find the proportion of centres that are performing PCR tests, and testing for Panton-Valentine Leukocidin producing *Staphylococcus aureus*.
Calculate the proportion of children testing positive for: at least one micro-organism; and each specific micro-organism (using conventional techniques, ie not PCR).
- 1E:** Describe the combinations of blood-tests carried out at presentation and summarise the test results. Find the proportion of children with elevated results for each blood-test type at presentation (results above centre-specific normal ranges), and the proportion of children with CRP_{max} occurring at presentation. Describe the types of samples.
- 1F:** Summarise CRP_{max} by age-group and micro-organisms detected.
- 1G:** Describe the imaging methods routinely used to aid diagnosis. What proportions of each method gave an abnormal result..
- 2A:** Describe the clinical time-line for antibiotic treatment (specifically when antibiotics are started) Describe the types of antibiotic regimes prescribed. Summarise the number of different antibiotics given as initial treatment, and the total number of different antibiotics patients receive over the durations of treatment by each route. Summarise the numbers of children being given different types of regime: early vs

normal length of time to oral switch; dosage – how many were given normal doses throughout; shortened vs standard length of time on antibiotics.

- 2B:** Describe the IV and oral antibiotics prescribed during hospital stay. For each antibiotic: which were prescribed at least once; which were part of the initial treatment; what was the average daily dose; with what frequency were doses given; and was the duration greater than 1 week. Were there differences in initial IV antibiotic prescriptions between secondary and tertiary site types; between children with and without penicillin allergy; and with and without sickle cell disease?

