Any children not falling into any of these categories will be excluded from the analysis.

Definitions

1. Simple cases

Children presenting with SA or OM for the first time, and with no chronic comorbidities. Specifically:

- No orthopaedic surgery 6 months prior to presentation on same limb/joint
- No chronic co-morbidities (sickle cell disease, known immunocompromise, indwelling central venous catheter or PICC, cystic fibrosis, or cerebral palsy).

2. Complex cases

Children presenting with SA or OM who already have a diagnosis of SA or OM and/or have chronic comorbidities, but who are not presenting because of an infected implant from previous orthopaedic surgery. Specifically:

- Not presenting because of an infected implant
- Any orthopaedic surgery in 6 months prior to presentation on same limb/joint
- Any chronic co-morbidities (sickle cell disease, known immunocompromise, indwelling central venous catheter or PICC, cystic fibrosis, or cerebral palsy).

3. Infected implants

Children presenting with SA or OM who already have a diagnosis of SA or OM and who are presenting because of an infected implant from previous orthopaedic surgery.

4. Incorrect diagnosis of SA/OM

Some children captured by the database were treated for SA/OM but were later found to have a different diagnosis.

Completeness of follow-up

Follow-up data are collected at a follow-up visit at around 3 months post discharge. The number lost to follow up will be reported and the reasons where known will be documented. Any deaths and their causes will be reported separately.

Study Outcomes

This study examines many measurements routinely made in the diagnosis, treatment, and aftercare of children with SA or OM. There are three areas of key interest: Diagnosis (Objective 1); Treatment (Objective 2); and Complications Arising and/or Treatment Failures (Objective 3). The key endpoints are:

Diagnosis:

- Bones and joints affected
- Time taken from first presentation to:
 1. Referral to hospital
 2. Having surgery
 3. Initiation of IV antibiotics [this time-point used also as a proxy for a diagnosis being made]
- Surgical procedures carried out prior to diagnosis
- Imaging types used (X-ray, CT scan, ultrasound, bone scan, MRI), and results obtained
- Diagnostic blood tests carried out (Hb, WBC, N, Plt, CRP, ESR) and their outcomes
- Microbiological tests carried out (presence of any of 8 named micro-organisms)

Antibiotic Treatment in and post hospital stay:

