The number and percentage of types of sample for micro-biological testing (e.g. blood, pus, etc.) that are typically taken from children will be reported [see Table 1D-2].
- [1E] The number and percentage of cases with test results at presentation for: each of 6 blood tests; and the combinations ‘CRP & ESR’ and ‘CRP & no ESR’ will be reported, split by centre type (Tertiary / Secondary) [see Table 1E-1]. A boxplot for each of the six blood test measures at presentation will be created to show the distribution of results. Proportions with elevated results (above centre-specific normal ranges) will be calculated for each blood test type [see Table 1E-2].

The blood test result ‘CRP_{max}’ will be summarised for culture-positive and culture negative cases and a box plot created to compare these. This analysis will be split by age-group. This is to explore whether a higher CRP_{max} is associated with particular organisms. Differences that are clinically significant will be tested for statistical significance using appropriate hypothesis tests [see Table 1E-3].
- [1F] There are five imaging methods that could be requested by clinicians to aid diagnosis. The number and percentage of cases for each imaging type used prior to diagnosis will be reported, split by centre type (Tertiary / Secondary) and of these the number and percentage abnormal [see Table 1F-1].

Objective 2

Treatment of children with SA or OM takes the form of antibiotic treatment and additionally for some cases, surgical intervention. Initially antibiotics are given intravenously. At a later date, antibiotics are given orally – the timing of the switch is based on clinical judgement that the child has recovered sufficiently and is capable of taking drugs orally.

- [2A] The lengths of time on IV antibiotics, oral antibiotics, and total antibiotic duration will be summarised using appropriate descriptive statistics. (Note that these times are based on what happened during hospital stay and what was **planned** at discharge. It is not possible to obtain data for the actual date when antibiotics were stopped post discharge.) Results will also be split by centre type, whether there was at least one surgical procedure after initiation of IV antibiotics, if CRP_{max} occurred at presentation, and by microbes detected. [See Table 2A-1].

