Other

Infection History in the last 12
calendar months?

Pneumonia

Septicaemia

Pyelonephritis

Cellulitis / soft tissue infection

Meningitis

Osteoarticular infection

Abdominal sepsis

Varicella

Other

History of Trauma in the last
month?

Other Surgery in 12 months prior to
presentation?

Pre-presentation variables that affect drug choice, dosage and duration. (Simple cases only)

TABLE 1A-7

Antibiotic Medical History	N(%)	Route		Duration
		IV	Oral	> 1 week
Penicillin allergy		-	-	-

Antibiotics (1 month
pre-presentation)

Any

Flucloxacillin

Clindamycin

Cefuroxime

Ceftriaxone

Amoxicillin

Co-Amoxiclav

Rifampicin

Vancomycin

Fusidic Acid

Teicoplanin

Other

1B: The clinical time-line for diagnosis

TABLE 1B-1

Diagnostic and hospital stay Time-line (Days)	Appropriate Summary Statistics
From first presentation to:	
Hospital Referral	
1 st Imaging	
Pre-diagnosis surgery	
Radiological diagnosis	
Initiation of IV antibiotics	
(proxy for diagnosis of OM/SA)	

1C: Surgical procedures carried out post presentation and prior to diagnosis (before or on the same day as initiation of IV antibiotics).

TABLE 1C-1

Surgery types	Rate n (%)
Any	
Aspiration	
Incision and drainage	
Drill decompression	
Curettage/excision	
Arthrotomy	
Arthroscopy	
Amputation	

Debridement

Fasciotomy

Compartment decompression

Secondary closure

Skin graft

Other plastic surgery

1D: Summary of range of tests carried out and sensitivity of conventional microbiological tests. (Simple cases only)

TABLE 1D-1

N(%)
Children with at least one conventional test carried out
At least one micro-organism detected
Specific mirco-organisms detected by conventional testing:
Staphylococcus Aureus
PVL tested for?
Kingella Kingae
Streptococcus pyogenes
Pseudomonas
Group b Streptococcus
Salmonella
Candida
Tuberculosis
Other
PCR testing carried out

Types of sample used for conventional microbiological testing. (Simple cases only)

TABLE 1D-2

N(%)

Number of different
sample types taken

0

1

2

>2

Sample types. Children
that had at least one:

Pus (periosteal)

Bone biopsy

Pus/Wound swab

Joint aspirate

Other

1E: Blood-tests carried out at presentation. (Simple cases only)

TABLE 1E-1

Blood tests at presentation	N(%) with at least one measurement on day of presentation	Summary statistic for test results	% with elevated* results
Hb			
WCC			
N			
Plt			
CRP			
ESR			
CRP & ESR		-	-
CRP & not ESR		-	-
CRP _{max} occurring at presentation		-	-

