*Above the centre specific normal range

1F: Comparing average CRP_{max} for each culture negative vs. positive, by age-group. (PCR and conventional test results combined; Simple cases only).

TABLE 1F-1

Microbe	Summary statistics for CRP _{max}					
	< 1 year		1-6 years		6-16 years	
	+ve	-ve	+ve	-ve	+ve	-ve
Staphylococcus Aureus						
Kingella Kingae						
Streptococcus pyogenes						
Pseudomonas						
Group b Streptococcus						
Salmonella						
Candida						
Tuberculosis						
Other						

1G: Imaging types routinely used to aid diagnosis (On day of or prior to initiation of IV; Simple cases only).

TABLE 1G-1

Imaging Type	N(%) with at least one image	Number (%) Abnormal
X-ray		
CT scan		
Ultrasound		
MRI		
Bonescan		

What is the range of durations of intravenous and oral antibiotics used to treat osteomyelitis?

2A: The clinical time-line for antibiotic treatment.

TABLE 2A-1

Antibiotic Treatment Time-line (Days)	Appropriate Summary Statistics
Length of time on:	
IV	
Oral ^(a)	
Total ^(b)	

^(a)Use time on oral antibiotics pre-discharge plus planned duration, as proxy for actual duration.

^(b) Length of time treated with any antibiotic (for some children oral antibiotics were given concurrently to IV. So the Total length of time is not necessarily the time on IV plus the time on Oral)

Types of antibiotic regimes experienced.

TABLE 2A-2

Antibiotic Regime	All	Centre Type	
		Tertiary	Secondary
Number of different antibiotics given at initiation of treatment			
1			
2 or more			
Timing of oral switch			
Very Early (< 1 week)	Also report median & IQR		
Early (1-2 wks)	for each category		
Standard / Late (> 2 wks)	here		

Total course of antibiotics

Shortened (< 6 weeks)

Standard (> 6 weeks)

DoseAugmented at least once^(a)

Standard throughout

**Total number of antibiotics
prescribed****IV:**

1

2

>2

Oral:

1

2

>2

^(a)At least one IV antibiotic given at a high dose

2B: IV and oral antibiotics prescribed prior to discharge.

TABLE 2B-1

Antibiotic	Given at least once	Part of initial prescription	Daily dose per kg weight of child	Frequency					Duration (> 1 week)
				6 hourly	8 hourly	12 hourly	Once daily	Other	
IV									
Flucloxacillin									
Clindamycin									
Cefuroxime									
Ceftriaxone									
Other									
Oral									
Flucloxacillin									
Clindamycin									
Amoxicillin									
Co-Amoxiclav									
Rifampicin									

Other

TABLE 2B-2

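### Blood tests at presentation are classified only as above range, even haemoglobin, so low values are pooled with in-range ones

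*SAP*

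**What the plan says.** The rule is stated three times, consistently.

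- Study Objectives, sub-objective 1E: "Find the proportion of children with elevated results for each blood-test type at presentation (results above centre-specific normal ranges".
- Analysis, Objective 1, [1E]: "Proportions with elevated results (above centre-specific normal ranges) will be calculated for each blood test type".
- Appendix A, Table 1E-1: one column for the percentage "with elevated* results", with a footnote defining the starred word as "Above the centre specific normal range".

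The tests covered are listed among the key diagnosis endpoints in Study Outcomes: "Diagnostic blood tests carried out (Hb, WBC, N, Plt, CRP, ESR) and their outcomes". Table 1E-1 lists the same six, with white cells labelled WCC rather than WBC.

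Two other displays of the same results are planned. Table 1E-1 has a column headed "Summary statistic for test results", and [1E] adds: "A boxplot for each of the six blood test measures at presentation will be created to show the distribution of results". Under Objective 2, [2C] plans further boxplots of each test over time, starting at presentation.

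**The concern.** A rule that looks only above the upper limit fits a test whose departure from normal is a rise, as with CRP and ESR. It fits Hb poorly, because the result a reader would want to pick out is a low one. It fits white cells, neutrophils and platelets only in part, because they can leave the range in either direction.

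This is a descriptive study, so its tables are its product. Objective 1 asks about the clinical, biochemical and radiological criteria used in diagnosis, and the blood tests and their outcomes are a listed key endpoint. As planned, the report could not say what share of children presented with Hb or a cell count below their centre's range. The Hb entry in the elevated column would carry little information.

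The template for 1E is headed for simple cases only. The other groups are to be analysed separately as a secondary analysis, and the complex group includes children with sickle cell disease or known immunocompromise. If the same layout is reused there, the omission carries over to children for whom low values may matter more.

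**Working it through.** The SAP states no figure to reproduce. The check is of a category definition, made by comparing the places where it appears.

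**Step 1: is the rule really meant for Hb?** Sub-objective 1E and analysis [1E] both apply it to each blood test type. In Table 1E-1, cells that do not apply are dashed out: the two CRP/ESR combination rows and the row for the maximum CRP occurring at presentation have a dash in the elevated column. The Hb, WCC, N and Plt rows have none. The template therefore distinguishes applicable from inapplicable cells and leaves Hb among the applicable ones. A slip in one place is unlikely, since text, table and footnote agree.

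**Step 2: what does the proportion leave together?** For any one test, among children measured:

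% above + % within + % below = 100, so % not elevated = 100 − % above = % within + % below.

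If the Hb row shows *a*% elevated, this column alone allows the share below range to be anything from 0% to (100 − *a*)%. The same holds for WCC, N and Plt.

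**Step 3: do the other displays recover the missing share?** If every child shared one lower limit, a reader could set that limit against the pooled quartiles and get a rough bound. For example, a lower quartile under the limit would mean that at least 25% were below range. The SAP itself says the ranges are centre-specific. The boxplots are described by test, with no split by centre, and the sample runs from birth to 16 years. The planned scale is: "It is estimated that at least 500 cases will be accrued by around 50 centres over a 6-12 month period". There is then no single limit to draw on the plot. The displays show that low values exist and how low they go, but not how many children were below their own centre's limit.

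**Step 4: is a below-range or out-of-range percentage planned elsewhere?** No. Table 2C-1, on tests just before oral switch, gives numbers tested, summary statistics and CRP relative to its maximum, without any classification against the normal range. By contrast, the imaging tables (1G-1 and 2F-1) report the number and percentage abnormal.

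**Step 5: what depends on the proportion?** The associations under Objective 3 use regime type, surgery type, treatment failure and any complication. The comparison under [1E] that may lead to hypothesis tests uses maximum CRP. Neither uses the elevated proportion.

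**Size.** The SAP gives no expected distribution for any blood test, so the number of children affected cannot be derived.

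**The case against.** The strongest reply is that the column does what it says. It is headed elevated, its footnote defines the word exactly, and it counts elevated results. It makes no claim to measure abnormality. The SAP's interest in blood tests is mainly in CRP, alone, with ESR, or at its maximum, and nothing in it makes a low Hb or a low count a diagnostic criterion or an outcome. Low values also remain visible: the summary-statistic cells are open for all six tests, and boxplots are planned at presentation and over time. If many children had low Hb, the summary statistic in the same row would be expected to reflect it.

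Much of this stands. A reader might infer that the SAP reports low results as not abnormal, or that the column understates abnormality. The document does not support either reading: it never labels a non-elevated blood result as normal, and for test results it uses the word abnormal only for imaging. A reader might also infer that the Hb entry must be near 2.5%, the share above the upper limit of a central 95% reference range in healthy children. The SAP does not say that the ranges are 95% limits or that they are matched to age, so that figure cannot be taken from it.

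The reply does not justify applying the rule to Hb. Having chosen to compare all six tests with the normal range, the plan makes the comparison in the less useful direction for one test and in one of two relevant directions for three others. The pooled displays cannot supply the missing percentages, for the reason in step 3.

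**Conclusion.** The point holds as a limited one. The only normal-range classification planned for blood tests at presentation is above range, for every test including Hb. Low Hb and low white cell, neutrophil or platelet counts are never counted as out of range and are pooled with in-range results. The summary statistics and boxplots show low values without classifying them against centre-specific limits.

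The consequence is small. There is no contradiction in the rule itself, which is the same wherever it appears. No hypothesis test or treatment-failure analysis is affected. What is lost is a simple and useful percentage in a descriptive table on a listed key endpoint. The conclusion assumes that a below-range Hb or cell count is worth telling apart from an in-range one. This is a judgement about usefulness, which the SAP does not address.

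**What to change.** In sub-objective 1E, analysis [1E] and Table 1E-1 with its footnote:

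- Hb: report the percentage below the centre-specific lower limit.
- WCC, N and Plt: report the percentage below and the percentage above.
- CRP and ESR: keep the percentage above.

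First confirm that lower limits are held. The SAP refers to normal ranges, which suggests that both limits exist, but its Data Collection section does not list ranges among the items recorded. If lower limits were not captured, say so in the table footnote and leave the Hb cell of the elevated column dashed.

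The cost is one extra column and that check. In the same edit, correct the pointer in [1E]: it sends the elevated proportions to Table 1E-2, which the appendix does not contain, whereas the column sits in Table 1E-1.

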- Length of time on IV antibiotics
- Length of time on oral antibiotics
- Total length of time on antibiotics
- Length of time from presentation to discharge
- Blood tests carried out and their results
- Antibiotics prescribed (during hospital stay and at discharge)
- Dosage (Normal / High as defined in Children's British National Formulary)
- Adherence to discharge prescription
- Reasons for non-adherence or changes to prescribed regimes.

Complications / Failure of treatment

- Complication types
- Actions arising from complications
- Treatment failure (Y/N)

Analysis

The primary interest are the sub-group of children with acute SA / OM and no chronic comorbidities (simple cases). All analyses described below will therefore be carried out for this sub-group in the first instance. The other two sub-groups (chronic SA/OM and infections arising from previous orthopaedic surgery) will be analysed separately as a secondary analysis. See *Appendix A: Template Results Tables* for tables referred to in the following analysis plan.

Objective 1

- [1A] See Section 8.2 above for demography and definition of diagnosis groups. Numbers and percentages will be calculated and results tabulated separately for: demographics; diagnosis groups; presentation; history of orthopaedic surgery; medical history; and antibiotics prescribed prior to presentation. See Tables 1A-1,2,3,4,5,6 below
- [1B] The clinical time-line from first presentation through to diagnosis will be explored. Time to hospital referral, first imaging, surgery, radiological diagnosis, and initiation of IV antibiotics will all be summarised using appropriate descriptive statistics [see Table 1B-1].
- [1C] The number and percentage of cases undergoing different types of surgery prior to diagnosis will be reported [see Table 1C-1].
- [1D] The number and percentage of cases testing positive for at least one micro-organism, and each of 8 unique micro-organisms will be reported, split by centre type (Tertiary / Secondary). Any other micro-organisms detected will be categorised and reported as “Other”. Of cultures testing positive for *Staphylococcus aureus*, the number and percentage where PVL is tested for will be reported. The number and percentage of cases where a PCR test is also carried out will be calculated by centre type. [See Table 1D-1].

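### CRPmax differences are tested only after they have been seen and judged clinically significant, with no threshold or multiplicity rule, so p-values for the tests that are run lack their nominal level

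*SAP*

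**What the plan says.** Item [1E] under Objective 1 of the SAP's Analysis section says that CRPmax "will be summarised for culture-positive and culture negative cases and a box plot created to compare these". It adds: "This analysis will be split by age-group". The purpose is exploratory and organism-specific: the sentence beginning "This is to explore whether a higher CRP" asks whether higher maximum values go with particular organisms. The testing rule follows: "Differences that are clinically significant will be tested for statistical significance using appropriate hypothesis tests".

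The SAP does not say how large a difference must be to count as clinically significant, who judges it, or whether the judgement precedes sight of the data. It names no test, level, sidedness or adjustment.

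Item [1E] refers to a Table 1E-3 that Appendix A does not contain. The CRPmax template there is Table 1F-1, headed as a comparison "for each culture negative vs. positive, by age-group" with "PCR and conventional test results combined; Simple cases only". Its rows match item [1D], where "each of 8 unique micro-organisms will be reported" and a ninth category takes the rest ("Any other micro-organisms detected will be categorised and reported as" Other). Its columns are three age groups, each split into positive and negative.

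**The concern.** The gate and the test use the same quantity. A contrast is tested because its observed difference is large, and the test then asks whether that difference is large relative to its standard error. Among contrasts with no true difference, those that reach a test are the ones chance has already pushed apart, so the usual 5% level does not apply to them.

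A second, separate problem is the number of comparisons open to testing without adjustment. A third is that the arms are not fixed. The prose speaks of culture results, whereas the table heading adds PCR, so a child positive by PCR alone is negative under one and positive under the other.

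At stake is whether a reported link between an organism and high CRPmax can be taken at its stated p-value.

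**Working it through.** The SAP gives no error rate, power or effect size for this analysis, so there is no figure of its own to reproduce.

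**Number of contrasts.** Eight named organisms plus Other make 9 rows; the age groups (under 1, 1–6 and 6–16 years) make 3 columns of pairs. 9 × 3 = 27 candidate contrasts. If the prose means only any-positive against negative within each age group, there are 3. The interest in particular organisms and the layout of Table 1F-1 favour 27.

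**Level of a test that is run.** Assume a two-sided 5% normal test, run only if the observed difference exceeds c standard errors, with no true difference. For c up to 1.96, every result with p < 0.05 also passes the gate, so

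P(p < 0.05 | tested) = 0.05 / P(|Z| > c).

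- c = 0 (no selection): 0.05 / 1 = 5.0%
- c = 0.5: 0.05 / 0.6171 = 8.1%
- c = 1.0: 0.05 / 0.3173 = 15.8%
- c = 1.5: 0.05 / 0.1336 = 37.4%
- c = 1.96 or more: 100%

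The values of c are assumptions. A threshold fixed on the CRP scale gives a different c in each cell. For example, take a threshold of 0.5 SD with assumed cells of 10 positive and 50 negative: the standard error is √(1/10 + 1/50) = 0.346 SD, c = 0.5 / 0.346 = 1.44, and the rate is 0.05 / 0.1489 = 33.6%. A simulation of 20,000 runs gave the same figure.

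**What selection does not do.** The unconditional chance that a null contrast is both selected and has p < 0.05 is 5% for c up to 1.96 and below 5% beyond that. With assumed cells of 20 and 80 and the same 0.5 SD threshold, c = 0.5 / 0.25 = 2.0, and only 4.55% of null contrasts are selected at all.

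**Number of unadjusted contrasts.** With the level assumed to be 0.05 and contrasts treated as independent:

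- 27 contrasts: 27 × 0.05 = 1.35 expected false positives; 1 − 0.95^27 = 75.0% chance of at least one
- 3 contrasts: 1 − 0.95^3 = 14.3%
- 27 contrasts at a level of 0.01 or 0.10: 23.8% or 94.2%

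When negatives are shared across organisms (simulated with cells of 10 and 50), the 75.0% becomes 73.2%. Selection at up to 1.96 standard errors does not change these figures.

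**The case against.** The strongest reply is that requiring a difference to be both clinically large and statistically significant cannot produce more false claims than testing everything. That is correct. A reader might infer that selecting before testing itself generates extra false organism associations, or that the p-values carry no information. The plan does not support either inference: the inflation applies to the tests that are run, and the family-wise excess comes from the number of contrasts. Table 1F-1 also shows summary statistics for every cell, so untested comparisons stay visible. That softens the selection but does not restore the level of the p-values reported.

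The SAP does not say that the judgement rests on observed differences. It is nevertheless the only workable reading, because summaries and plots come first and no threshold is set beforehand.

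A reader might also infer that each negative column contains children positive for other organisms. The SAP leaves negative undefined: it could mean negative for that organism or nothing detected, and either is a legitimate comparator once stated. Nor does the SAP give organism frequencies, so it cannot be asserted that most cells will be small. Some may be empty and yield no test, so 27 is an upper count.

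Finally, the analysis is exploratory, sub-objective 1F asks only for a summary, the template has no p-value column, and no key endpoint depends on these tests. This stands and limits the severity.

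**Conclusion.** The point holds in a limited form. Item [1E] sets a rule under which tests are chosen on the quantity they test, so p-values for the tests that are run do not have their nominal level. The conditional rejection rate for a true null is about 8%, 16% or 37% at assumed selection thresholds of 0.5, 1.0 or 1.5 standard errors; the direction is certain for any threshold above zero, but the size depends on a threshold the SAP does not give. Independently of selection, unadjusted testing carries a chance of at least one false positive of about 75% over 27 contrasts, or 14% over 3, assuming a 5% level, independence and populated cells. The definitions of positive and negative also need to be made consistent. Severity is low to moderate: no primary conclusion rests on this analysis, but a p-value from a test chosen by its own result should not be reported as an ordinary one.

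**What to change.** Delete the sentence on testing. For every organism-by-age contrast in Table 1F-1 with enough data, report the estimated difference in CRPmax, or the ratio of geometric means, with a 95% CI, whatever its size, labelled exploratory and unadjusted for multiplicity. Fix the minimum cell count in advance so that inclusion depends on numbers and not on the result. This matches items [3B] and [3C], which already report associations as estimates with 95% CIs.

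If p-values are kept, give them for all contrasts with a stated adjustment. Bonferroni over 27 would use 0.05 / 27 = 0.00185 per test, with a family-wise rate of 1 − (1 − 0.00185)^27 = 4.9% under independence.

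In both item [1E] and Table 1F-1, use one definition of positive (culture alone, or culture or PCR) and one of negative, and correct the table reference. A single regression with a global test for organism is optional. It would need a rule for children with two organisms and, without an organism-by-age interaction, would not give the age-specific comparison the SAP asks for.

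The cost is a wording change, slightly more tabulation and fewer headline p-values.
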